3.4 Study Contacts in the Treatment Period with Control-IQ 2.0 Technology

Participants will have a phone (or video-conference) follow-up visit at 1 day, 3 days and 1 week, a clinic follow-up visit at 2 weeks, a phone follow-up visit at 3 days and 1 week after switching glycemic targets, and a final clinic visit at 2 weeks after switching glycemic targets, within the windows specified below.

TARGET DAY/WEEK	VISIT OR PHONE	TARGET WINDOW (AROUND TARGET DAY/WEEK)
Visit 6: Control-IQ 2.0 Training Visit	V	2 weeks (±3 days) after Visit 2
Visit 7: 1 days after visit 6	P	+12 hours
Visit 8: 3 days after visit 6	P	+ 1 day
Visit 9: 1 week after visit 6	P	+ 2 days
Visit 10: 2 weeks after visit 6 (switch targets)	V	+ 3 days
Visit 11: 1 day after visit 10	P	+12 hours
Visit 12: 3 days after visit 10	P	±1 days
Visit 13: 1 week after visit 10	P	+ 2 days
Visit14: 2 weeks after visit 10	V	+ 3 days

- If necessary, visits should be completed out-of-window rather than missed. A visit is not considered
- missed until the next visit/phone window opens.
- The goal will be for all participants to complete all scheduled visits. However, participants who
- 384 (because of unforeseen circumstances or due to changes in contact precautions that may be needed
- during the evolving COVID-19 pandemic) are unable or unwilling to return for all follow-up visits
- will be permitted to return for key visits only (Visits 1, 2 and 6) as an alternative to withdrawal from the
- study. Remote (phone) visits will still be performed as scheduled. When a participant is placed into this
- status, remote visits for visits 10 and 14 will not be recorded as protocol deviations.
- Additional phone and office visits may occur as needed.
- For the in clinic visits at the end of each two week treatment period, if a clinical site believes these visits
- need to be performed remotely, the following approvals must be obtained prior to conducting the visit
- remotely:

- Sponsor approval for the reason the visit cannot be performed in person
 - Investigator approval at the site level for the reason the visit cannot be performed in person
- In addition, all study procedures listed in section 3.4.1 are to be completed, including upload of the study device and review of the device data. If the final visit is performed remotely, participant will mail in their study devices, and investigators will remotely supervise transition back to their home diabetes treatment
- 398 plan.

399

416

417

418

419

420

421

422

3.4.1 Procedures at all Study Visits

- 400 The following procedures will be performed at each visit, unless otherwise specified:
- Review of study device data
- Assessment of compliance with study device use by review of any available device data
- Assessment of device issues that have occurred
- Assessment of adverse events, using open ended questions to capture hyperglycemic and
 hypoglycemic events, and their underlying cause and relationship to the study device or other parts of
 the system (such as the infusion set).
- Review of ongoing study late bolus meal challenges when in the treatment period
- Baseline INSPIRE questionnaire for pediatric participants age 8-17, for adult participants age 18+, and for parents of pediatric participants age 2-17 will be completed at visit 6
- Post Assessment INSPIRE questionnaire for pediatric participants age 8-17, for adult participants age 18+, and for parents of pediatric participants age 2-17 will be completed at visits 10 and 14
- SUS Scale will be completed at visits 10 and 14
- Study Specific Questionnaire will be completed at visits 10 and 14
- At the final visit (or at subject withdrawal), the study staff will then supervise the participants transition back to their standard of care therapy as follows:
 - Study staff will re-evaluate the subject's baseline therapy doses, noting changes in basal rates, carbohydrate ratios, and correction factors in use at the end of the trial. For prior CSII users, the study investigator will supervise and confirm the entry of settings in the insulin delivery profile of the participant's home pump at the end of the study.
 - For those subjects using basal insulin, doses will be adjusted to best match the current daily insulin requirements from CSII use, typically = (total daily dose + 20%)/2, with further modification as per clinical site usual practice.
- Participants must have two CGM or fingerstick BG values, separated by at least 15 minutes, that must be above 80 mg/dL prior to discharge from the clinic for the final visit. In addition, CGM trend arrow must not be going down at the time of discharge.
- Study staff will confirm subjects have carbohydrates on hand for their drive back home, and instruct subjects to check their glucose levels when they arrive at home, prior to bedtime, and at least one time overnight on the first night to monitor for hypoglycemia, reminding subjects that insulin on board can be active for the next few hours even after stopping their pump.

430	3.5 Unscheduled Visits
431 432	Participants may have unscheduled visits during the study period if required for additional device training or other unanticipated needs per the study investigator discretion.
433	3.6 Late Bolus Meal Challenges
434 435	Participants will complete two late bolus meal challenges during each two week treatment period. Procedures are described in section 5.1.
436	3.7 Adjustments in Insulin Pump Settings
437 438 439	Insulin and glucose data from the screening visit, as well as follow up visits, will be reviewed and the site investigator may adjust insulin delivery profile settings as needed in accordance with their clinical practice.
440	3.8 Early Discontinuation of Study Device
441 442 443 444 445	If the participant cannot be reached for scheduled study contacts, the participant's other contact methods will be utilized. Participants who are not compliant with the arranged contacts on two separate occasions may be discontinued at the discretion of the investigator. Participants who discontinue the study device prior to the final visit, either by choice or by investigator decision, will be asked to come for an end of study visit and then will be dropped from the study.
446	3.9 Remote Monitoring
447 448 449 450	Real-time CGM alerts will be sent to study staff providers (MD, DO, NP, PA) for the first ten 6-13 year old participants to begin use of the lower target (90-130 mg/dL) for the first week of Control-IQ 2.0 use at that target. This requirement will only be removed for future participants in this age group after the first ten participants finish the first week of use of the lower target, and no safety concerns arise, where:
451 452 453	 No severe hypoglycemia events related to algorithm delivered automated insulin dosing occur that required study staff intervention because the participant was not aware/treating appropriately.
454 455 456	 No severe hyperglycemic events related to algorithm delivered automated insulin dosing occurred that required study staff intervention because the participant was not aware/treating appropriately.
457 458	In addition, real-time CGM alerts will be sent to study staff providers (MD, DO, NP, PA) for all 2-5 year old participants throughout their use of Control-IQ 2.0 technology (all 4 weeks).

459	Chapter 4: Study Devices and Drugs
460	4.1 Study Devices
461	4.1.1 Insulin Pump
462 463 464	For the run in period, participants will use a study provided Tandem t:slim X2 with Control-IQ 1.5 technology (Investigational Device). For the treatment period, participants will use a study provided Tandem t:slim X2 with Control-IQ 2.0 technology (Investigational Device).
465	4.1.2 Continuous Glucose Monitoring
466 467	The study CGM is the commercial version of the Dexcom G6, which includes a transmitter and sensors. The CGM sensor will be replaced at least once every 10 days.
468	4.1.3 Blood Glucose Meter
469	The study blood glucose meter is the Contour® NEXT (Ascencia Diabetes Care).
470 471 472	Blood glucose levels will be measured using the study's blood glucose meter (glucometer) and the CGM device will be calibrated if needed using the study glucometer and strips in accordance with the manufacturer's labeling.
473	4.1.4 Ketone Meter
474 475	The study blood ketone meter is the Precision Xtra Blood Glucose and Ketone Monitoring System (Abbott Diabetes Care).
476 477	Blood ketone levels will be measured when needed to evaluate prolonged hyperglycemia. The blood glucose meter component of the Precision Xtra device will not be used.
478	4.2 Study Device and Drug Accountability Procedures
479 480	Device accountability and inventory will be documented to include detailed inventory records of the study CGM supplies, and Tandem insulin pump system.
481	4.3 Participant Access to Study Device at Study Closure
482 483 484	Participant will return all investigational study devices and supplies (insulin pump, CGM and related supplies) at study closure. Participant may keep the study ketone meter and study glucometer if these devices are not marked for investigational use only.

Chapter 5: Testing Procedures and Questionnaires

486	5.1 General Challenge Guidelines
487 488 489	All study participants will complete two late bolus meal challenges during each two week treatment period. Participants will be instructed to wait at least 48 hours after switching targets in the treatment period to perform the next set of challenges.
490	A minimum of 48 hours will occur between all challenges for each participant.
491 492 493	A paper logbook will be provided to participants that includes a page to record details about each challenge and procedural instructions about how participants will conduct these challenges. This material will be reviewed with each participant, and will be used for source verification for the eCRF database.
494 495 496 497 498	Before starting each challenge, participants (or parent/guardian if the participant is < 18 years of age) must assure the participant has a working CGM and Control-IQ is active. For pediatric participants, the participant's parent or guardian must remain with the child at all times and monitor CGM readings frequently during and through meal completion plus 5 hours (3 hours for participants age 2-5). Snacks and glucagon must be available for use during and after each challenge.
499 500 501 502	Participants will be instructed to communicate with study staff within one day prior to each challenge to review procedures and to have a contact with study staff no more than 1 day after the completion of each challenge. The participant or parent/guardian must have an on-call phone number for the study team prior to initiation of each challenge.
503 504	Hyperglycemia and Hypoglycemia treatment guidelines (sections 3.1.3 and 3.1.2) remain in effect for the challenges, and will be reviewed with participants prior to each challenge.
505 506	Site staff will directly contact the participant if they do not receive a follow up contact from participants when 24 hours have passed since the time of completion of the planned challenge.
507	5.1.1 Late Bolus Meal Challenges
508 509	All challenges will be performed with the last meal of the day (dinner) and participants will be instructed not to snack after dinner on days they are performing meal challenges, unless it is to treat hypoglycemia.
510 511 512	Participants will also be instructed not to use sleep activity for at least 5 hours (3 hours for participants age 2-5) once starting the meal challenge. Participants will be reminded to disable sleep activity if it is inadvertently activated during the challenge, and to re-enable it at the end of the challenge.
513	Time zero (start of the challenge) is at the first bite of food for the study meal.
514 515	During each two week treatment period with Control-IQ technology 2.0 use, the two meal challenges will consist of:
516 517 518	 Full bolus for the given carbohydrates and calculated correction, given 45 minutes after starting the meal, based on calculated bolus dose using the bolus calculator (with full amount of carbohydrates entered).
519 520 521	• Full bolus for the given carbohydrates and calculated correction, given 45 minutes after starting the meal, based on calculated bolus dose using the bolus calculator (with full amount of carbohydrates entered) AND enabling the late bolus feature to 45 minutes later.
522	For each meal challenge, participants will:
523 524	1. Be in a fasting state for two hours prior to consuming the last meal of the day, with the last manual insulin bolus more than two hours prior to the meal.

- 525 2. For participants age 6+, only begin the meal challenge if CGM glucose is between 70 mg/dL and 200 mg/dL, and CGM trend arrow is not down.
- For participants age 2-5, only begin the meal challenge if CGM glucose is between 70 mg/dL and 250 mg/dL, and CGM trend arrow is not down.
- 529 Subjects with hyperglycemia > 200mg/dL will reschedule their challenge for another time. If < 530 To mg/dL, carbohydrate treatment can be given, after which the meal challenge can continue.
 - 3. Pediatric participants age 2-5 should have a meal with at least 20 grams of carbohydrates. Participants age 6-13 should have a meal with at least 35 grams of carbohydrates. All other participants should have at least 50 grams of carbohydrates for the study meal challenges. *Each participant should use the same meal for all of their meal challenges in the study. Participants will be encouraged to use the same frozen entrée of their choice for consistency.*
 - 4. Do their best to complete the meal within 30 minutes of starting to eat.
 - 5. Write down the start and end time of eating the meal, as well as the meal content (to include amount of carbohydrate, protein and fat) on the study provided logbook.
 - 6. Bolus for the meal 45 minutes after starting to eat, entering the full carbohydrate amount and using the recommended dose from the bolus calculator. For one of the two challenges during a single treatment period, use the bolus calculator but do not change the bolus time. For the other challenge during the same treatment period, use the bolus calculator but change the bolus time to 45 minutes late.
 - 7. Not give an additional bolus during 5 hours (3 hours for participants age 2-5) after the start of meal challenge (i.e., after start of meal), unless BG is above 300 mg/dL for more than 1 hour, or symptoms of hyperglycemia develop.
 - 8. Not take additional carbohydrates during 5 hours (3 hours for participants age 2-5) after the start of meal challenge (i.e., after start of meal), unless BG is < 70 mg/dL, or symptoms of hypoglycemia develop.
 - 9. Not exercise for 5 hours (3 hours for participants age 2-5) after the meal challenge begins.
- 551 10. Make sure sleep activity is not active for the 5 hours (3 hours for participants age 2-5) after the meal challenge begins (start of meal).
 - 11. Notify the site within 24 hours after completion of each meal challenge.

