8.3 Sample Size

comparing continuous outcomes.

The sample size of at least 30 adults and adolescents age 14+ years old, 30 children age 6-13 years old, and 12 preschool participants age 2-5 years of age who will complete the trial was selected to have a reasonable time period of use in each age cohort to establish safety, with each subject completing 2 weeks of Control-IQ 1.5 technology use, 2 weeks of Control-IQ 2.0 technology use with the target of 112.5 to 160 mg/dL, and 2 weeks of Control-IQ 2.0 technology use with the target of 90-130 mg/dL. The choice of sample size is not based on statistical principles. In addition, the sample size assures a reasonable number of late bolus meal challenges completed.

There is a further enrollment goal of at least half of all participants in each age group have an HbA1c at baseline of $\geq 7.5\%$, and have at least 6 participants age 14-17.

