2. CGM hypoglycemia outcomes, compared between the three study time periods 922 a. Overall % time <54 mg/dL 923 b. Overall % time <70 mg/dL 924 3. Times in ranges-overall (70-180 mg/dL, >180 mg/dL, >250 mg/dL, 70-140 mg/dL) compared 925 between the three study time periods 926 4. Mean glucose compared between the three study time periods. 927 5. Overall variability (CV and SD) compared between the three study time periods 928 6. Secondary endpoints 2 - 5 compared during daytime and nighttime, across the three study time 929 930 periods 7. Secondary endpoints 2 - 5 as well as adverse events, during the study meal challenge periods, for 931 late bolus feature use compared to normal bolus in the meal challenges. 932 8. Time to intervention for hypo- or hyperglycemia during the study meal challenge periods, for late 933 bolus feature use compared to normal bolus in the meal challenges. 934 935 9. Number of interventions for hypo- or hyperglycemia during the study meal challenge periods for late bolus feature use compared to normal bolus in the meal challenges. 936 10. Subgroup Analysis for all metrics by age cohort, baseline HbA1c cohort (HbA1c at baseline of > 937 7.5%, yes/no), and target activity use (standard target, lower target, sleep activity, exercise 938 939 activity). 940 8.5 Analysis Datasets 941 942 Safety analysis set: All participants who initiate the Treatment Period and use the study device at least one time (including training). 943 CGM analysis set: Any member of the Safety Analysis Set who has at least 24 hours of CGM data during 944 945 either Treatment Period. CGM data occurring within the meal challenge windows (from time of start of meal up to 5 hours afterwards [3 hours for age 2-5]) will not be used to determine whether a subject is 946 included in CGM analysis set or not. 947 948 Late bolus meal challenge set: Any member of the Safety Analysis Set who has at least 24 hours of CGM data during the Treatment Period, and who has at least 3 hours of CGM data for at least one meal 949 challenge. 950 8.6 Analysis of Endpoints 951 8.6.1 Analysis of the Safety Event Endpoints 952 953

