8.7 Intervention Adherence

The following tabulations will be performed:

- Sensor use percent time of use as a function of overall treatment period
- Sensor use is defined as percent of time CGM is recorded as active (to include warmup) vs total study time.
- Closed loop system use percent time of use as a function of overall treatment period
- Closed loop system use is defined as percent of time closed-loop is recorded as active (to include pinning in sensor warmup) vs total study time.
 - Percent time in different operational modes as a function of overall treatment period
 - The investigational device allows for the following operational modes: standard target, lower target, sleep activity, and exercise activity.

For intervention adherence, overall treatment period is calculated from the start of the treatment period to the end of the treatment period where any gaps in CGM data are ignored.

1045	The following tabulations and analyses will be performed to assess protocol adherence for the study:
1046 1047	 Number of protocol deviations by site and by type, and number of unique subjects with each type of protocol deviation
1048	• Disposition summary (e.g., chart, table) accounting for all enrolled participants at each scheduled visit
1049	 Number of and reasons for unscheduled visits and phone calls
1050	• Number of participants who were enrolled but did not enter the Treatment Period and reasons
1051	 Number of participants who stopped treatment and reasons
1052	8.9 Baseline Descriptive Statistics
1053 1054 1055	Baseline demographic and clinical characteristics of the cohort of participants who initiate the Treatment Period will be summarized in a table using summary statistics appropriate to the distribution of each variable. Descriptive statistics will be displayed by treatment group for the following:
1056	• Age
1057	• Sex
1058	• Race
1059	• Ethnicity
1060	 Socio-economic factors (income, education, and/or insurance status)
1061	• Diabetes duration
1062	• HbA1c
1063	• BMI
1064	Total daily insulin
1065	• Prior severe hypoglycemia and DKA events in the last 6 months
1066	8.10 Additional Tabulations and Analyses
1067	The following data will be tabulated at baseline, for the run-in period, and for the two treatment periods.
1068 1069	• Insulin metrics (units/kg): total daily insulin, total daily basal insulin, total daily bolus insulin (plus total daily manual bolus, total daily automated bolus)
1070	8.11 Device Issues

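### For ages 2-5 the meal-challenge start rule gives two upper limits: begin at up to 250 mg/dL, but reschedule above 200 mg/dL

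*Combined protocol and SAP*

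**What the plan says.** Item 2 of section 5.1.1 (Late Bolus Meal Challenges) decides whether a family may go ahead with a challenge at dinner. It makes three statements about the upper limit, in this order:

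- Age 6 and over: "For participants age 6+, only begin the meal challenge if CGM glucose is between 70 mg/dL and 200 mg/dL".
- Ages 2 to 5: "For participants age 2-5, only begin the meal challenge if CGM glucose is between 70 mg/dL and 250 mg/dL".
- Then, with no age named: "Subjects with hyperglycemia > 200mg/dL will reschedule their challenge for another time".

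Both start windows also require that the CGM trend arrow is not pointing down. Section 5.1 provides a paper logbook that holds "procedural instructions about how participants will conduct these challenges" and serves as source for the eCRF.

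The results feed secondary endpoint 7 in section 8.4, which covers "Secondary endpoints 2 - 5 as well as adverse events, during the study meal challenge periods" and compares late bolus feature use with normal bolus. Section 8.8 tabulates "Number of protocol deviations by site and by type". Section 9.4 treats any failure to comply with the protocol as a deviation.

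**The concern.** A preschooler whose reading is above 200 but not above 250 mg/dL falls under two opposite instructions. One permits the start and the other postpones it. The protocol gives no order of precedence, and no other section states a start limit.

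This is a go/no-go threshold that parents apply at home, so it should have one answer. Three things are at stake, all modest:

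- **Deviation counts.** With up to 6 sites, a preschool start at 225 mg/dL could be recorded as compliant at one and as a deviation at another.
- **Consistency of the preschool data.** The analysed window opens at the start of the meal and lasts only 3 hours for ages 2-5 (section 8.6.4). A challenge begun above 200 mg/dL is above 180 mg/dL from time zero, so the limit applied affects time above 180 mg/dL and mean glucose in a small cohort that the synopsis says will also be analysed separately.
- **Safety.** The risk is small, because rescheduling is the safe fallback and several safeguards are in place.

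**Working it through.** The point rests on wording, so the first step is to set the instructions side by side. Assume the trend arrow is not down.

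| CGM reading before the meal | Age 6+: start window | Age 6+: reschedule sentence | Ages 2-5: start window | Ages 2-5: reschedule sentence |
|---|---|---|---|---|
| 70 to 200 mg/dL | may start | not triggered | may start | not triggered |
| above 200, up to 250 mg/dL | may not start | reschedule | **may start** | **reschedule** |
| above 250 mg/dL | may not start | reschedule | may not start | reschedule |

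Only one cell pair conflicts: ages 2-5, in a band 250 − 200 = 50 mg/dL wide.

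The second step is to see whether either reading removes the error:

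- If the 200 mg/dL sentence covers every age, the 250 mg/dL limit has no effect.
- If it covers only age 6+, the reader must supply a qualifier that is not there. Elsewhere in sections 5.1 and 5.1.1 the age 2-5 exceptions are written out, for example the 3-hour window and the 20 g carbohydrate minimum.

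The third step is the number of challenges under the rule. The inputs are planned minimum completers of 30 (age 14+), 30 (age 6-13) and "12 preschool participants age 2-5 years of age who will complete the trial" (section 8.3), and 2 challenges in each of 2 treatment periods, so 4 per participant (sections 5.1 and 8.6.4.1).

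- Ages 2-5: 12 × 2 × 2 = 48 challenges.
- By type, one of each per period: 12 × 2 × 1 = 24 with the late bolus feature and 24 with normal bolus.
- All ages: (30 + 30 + 12) × 4 = 288.
- Preschool share: 48 / 288 = 16.7%.
- Age 6+, unaffected: 60 × 4 = 240.

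The documents give no distribution of pre-meal glucose. For 12 completers, the number of preschool challenges that meet the conflict can therefore only be bounded between 0 and 48.

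The last step is whether the bolus comparison is biased. Item 6 says: "For one of the two challenges during a single treatment period, use the bolus calculator but do not change the bolus time"; in the other challenge of that period the bolus time is changed. Each child thus contributes one challenge of each type per period, and whichever start limit is used applies to both. Nothing in the text ties the choice of limit to the bolus type, so inconsistent use adds variability but has no direction. No sample size, power or alpha figure enters, since section 8.3 says the sample size has no statistical basis.

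**The case against.** The strongest reply is that the text has one sensible reading. Confining the reschedule sentence to age 6+ is the only interpretation that gives every sentence an effect, and it fits the deliberate preschool exceptions in the rest of the section. The 200 mg/dL sentence may simply not have been updated when the preschool limit was added. That is plausible, but it is inference: the protocol states no precedence, and the unqualified sentence comes directly after the preschool rule.

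Several points on weight are fair and stand:

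- The logbook and the monitoring plan are not among the documents. It is therefore not shown that families see the conflict or that sites would classify starts differently; both are possibilities.
- Starting glucose is not a criterion for the late bolus meal challenge set in section 8.5, so neither reading changes who is analysed or how endpoints are defined.
- The 48 challenges are a ceiling, not a count of affected ones.
- Safeguards are substantial: staff review procedures within one day before each challenge, a parent stays with the child and monitors CGM, an on-call number is required, hyperglycemia guidance stays in force, and providers receive real-time CGM alerts for all children aged 2-5 throughout Control-IQ 2.0 use (section 3.9).

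These limit the consequence. They do not remove the contradiction: the instruction for that band cannot be followed as written.

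**Conclusion.** The concern holds. For ages 2-5, readings above 200 and up to 250 mg/dL fall under two incompatible instructions, and the document does not resolve them. Confidence is high, because the conclusion depends only on the wording of item 2.

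The impact is low. At the planned minimum, exposure is at most 48 preschool challenges, with an unknown number actually in the band. Primary endpoints are untouched, and the comparison of late bolus feature with normal bolus is not biased. What remains is avoidable inconsistency in which preschool challenges go ahead and in how deviations could be counted. It should be corrected because it is an operational threshold and correcting it is cheap.

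**What to change.** Replace the reschedule sentence in section 5.1.1, item 2 with: *Age 6+: reschedule if CGM is above 200 mg/dL. Ages 2-5: reschedule if CGM is above 250 mg/dL.* If one limit for every age was intended, state 200 mg/dL once and delete the 250 mg/dL limit.

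Carry the same text into the challenge instructions in the participant logbook. If any preschool challenge has already begun above 200 and up to 250 mg/dL, classify it the same way at all sites in the section 8.8 deviation table.

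The cost is one sentence in the protocol, a check of the logbook instructions and the usual IRB approval of an amendment. Sample size, visit schedule and endpoints do not change.
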